PROTOCOL AB002

Multicenter, Randomized, Double-Blind, Placebo-Controlled, Proof of Concept Study of LSALT Peptide as Prevention of Acute Respiratory Distress Syndrome (ARDS) and Acute Kidney Injury (AKI) in Patients Infected with SARS-CoV-2 (COVID-19)

Investigational Product:	LSALT peptide
Indication:	LSALT peptide is indicated for prevention of acute respiratory distress syndrome and acute kidney injury in patients infected with confirmed COVID-19.
Phase:	2
Date:	June 9, 2020
Amendments:	1 (July 15, 2020) 2 (August 15, 2020) 3 (February 15, 2021) 4 (March 17, 2021)
Name and Affiliation of Principal Investigator (PI):	A list of the Principal Investigators is maintained in the trial master file
Name and Address of Sponsor:	Arch Biopartners Inc. [name]
GCP Statement:	This study will be performed in compliance with GCP, including the archiving of essential documents.

Confidentiality Statement

The information contained in this document is the property of Arch Biopartners Inc. All content are regarded as confidential and, except to the extent necessary to obtain informed consent or as required by law, may not be used, reproduced, or disclosed to third parties in any form whatsoever without written permission from Arch Biopartners Inc. Persons to whom the information is disclosed must be informed that the information is confidential and may not be further disclosed as above.

SYNOPSIS

TITLE: Multicenter, Randomized, Double-Blind, Placebo-Controlled, Proof of Concept Study of LSALT Peptide as Prevention of Acute Respiratory Distress Syndrome (ARDS) and Acute Kidney Injury (AKI) in Patients Infected with SARS-CoV-2 (COVID-19)

INVESTIGATIONAL PRODUCT: LSALT peptide

INDICATION: LSALT peptide is indicated for the prevention of ARDS and AKI in patients infected with confirmed COVID-19.

PHASE OF DEVELOPMENT: 2

INVESTIGATIONAL SITES/LOCATIONS: Multicenter

PRIMARY OBJECTIVE: To evaluate the proportion of subjects alive and free of respiratory failure (e.g., need for non-invasive or invasive mechanical ventilation, high flow oxygen [≥ 6 L/minute], or ECMO) and free of the need for continued renal replacement therapy (RRT) on Day 28. The need for continued RRT at Day 28 will be defined as either dialysis in the past 3 days (Day 26, 27, or 28) or an eGFR on Day 28 <10 mL/min/1.73 m².

SECONDARY OBJECTIVES: To evaluate the following:

- Incidence and time to mild, moderate, and severe ARDS per patient between treatment groups
- Ventilation-free days
- Time on nasal canula or oxygen mask
- 28-day mortality— both all-cause and attributable
- ICU length of stay (in days)
- Hospitalization length of stay (in days)
- Virologic clearance rate
- Incidence of other organ disorders
- Need and duration for extracorporeal membrane oxygenation (ECMO)
- Vasopressor-free days
- Clinical improvement in chest x-rays
- Change in baseline modified Medical Research Council (mMRC) dyspnea scale
- SOFA scores assessed periodically
- Change from baseline in liver function tests (ALT, AST, and total bilirubin levels)
- Change from baseline in SCr and eGFR
- Change from baseline in highly-sensitive troponin (hs-troponin)
- Change from baseline ACT, aPTT, and/or PT/INR levels
- Change from baseline for antiviral (SARS-CoV-2) immunoglobulins; IgG, IgM, and IgA at EOS.

HEALTH OUTCOMES OBJECTIVE:

- Total healthcare costs from admission to discharge.

EXPLORATORY OBJECTIVES: To evaluate:

- Change in serum cytokines including IL-1 α , IL-1 β , and ferritin levels, as well as other exploratory biomarkers.
- Change in baseline antiviral immunoglobulins (IgG, IgM, IgA) at EOS.
- Pharmacokinetics of LSALT peptide over the study period.

STUDY DESIGN AND METHODOLOGY: This study is a parallel group, randomized, third-party blinded, multicenter study to assess safety and efficacy of LSALT peptide *versus* placebo in hospitalized patients with confirmed infection or recent confirmed infection with complications associated with COVID-19.

Patients will be followed for safety and efficacy up to Day 28, with Day 1 being the day of randomization to assess safety.

After assessing the risk of ARDS and satisfying all inclusion and exclusion criteria, the patient will be randomized to 5 mg LSALT peptide or blinded placebo to be given intravenously once daily for a maximum of 14 days. Physical and respiratory examinations, vital signs, and adverse events will be recorded throughout the study, including Day 28 (EOS). Blood chemistries, hematology, coagulation, urinalysis, ECG, SARS-CoV-2 tests, eGFR, and chest x-ray (CXR) will be assessed at Day 1 (Screening/Baseline) prior to initiation of study drug, and on Day 3, EOT, and at EOS, as well as when clinically indicated. The ECG at EOS will only be obtained if clinically indicated. An additional CXR will be obtained at time of clinical improvement. Cytokines/biomarkers and pharmacokinetics (PK) will be assessed at Day 1 (Screening/Baseline) prior to initiation of study drug, at 1 (mid-dose) and 2 hours (end of infusion) of drug therapy on Days 1, 3, EOT, and a single blood sample at EOS for cytokines/biomarkers only. Where applicable, a urinary pregnancy test will be obtained at Screening in women of childbearing potential. Questionnaires (APACHE II, SOFA) will be obtained at Baseline, Day 3, EOT, and EOS; venous blood gas (VBG) or HCO₃ (bicarbonate) levels may be substituted for arterial blood gas (ABG) if it is considered standard-of-care (SOC) or in the patient's best interest, and results in comparable APACHE II and SOFA scores. Other questionnaires (Berlin Definition and modified Medical Research Council Dyspnea Scale) will be assessed at Baseline, Day 3, EOT, and EOS. IgG, IgA, and IgM antiviral antibodies will be collected at Baseline and EOS. Patients will be maintained on the SOC per institutional guidelines, including prophylaxis or treatment of VTE, throughout the study.

A Data and Safety Monitoring Board (DSMB) will evaluate patients on a continuing basis for primarily safety assessments. Per the DSMB Charter, the DSMB will meet at least monthly if not more frequently based upon enrollment throughout the study period.

NUMBER OF PATIENTS (PLANNED): Thirty (30) patients will be randomized to active drug (LSALT peptide) and 30 patients will be randomized to matching placebo. This study will be third-party blind with only the Pharmacist at the site unblinded for the purpose of preparing drug/placebo for injection.

DIAGNOSIS AND MAIN CRITERIA FOR INCLUSION:

Key Inclusion Criteria:

Eligible patients must fulfill the following inclusion criteria:

1. Male and female hospitalized patients between 18 and 80 years of age at time of consent.
2. Clinical and laboratory diagnosis of COVID-19 infection. Patients must be positive for the SARS-CoV-2 by Real-Time Reverse Transcriptase (RT)-PCR Diagnostic Panel or have an existing complication secondary to SARS-CoV-2 infection which was positive within 2 weeks of entry into the study. Further, patients must have at least two of the following three symptoms:
 - Fever (oral temperature $\geq 100.4^{\circ}\text{F}$ [$> 38^{\circ}\text{C}$]) with or without chills
 - Dyspnea or difficulty breathing (≥ 2 on mMRC dyspnea scale)
 - Nonproductive cough;
 - Or other signs and symptoms of established complications to SARS-CoV-2 infection (e.g., coagulopathy, cardiomyopathy, acute kidney injury [AKI], and/or acute liver injury) within the limits of Exclusion Criteria #8.
3. Patients must present with moderate to severe illness as defined below:
 - Moderate illness: Patients who have evidence of lower respiratory disease by clinical assessment or imaging and an oxygen saturation (SpO_2) $> 93\%$ on room air at sea level
 - Severe illness: Patients who have a respiratory frequency > 30 breaths per minute (bpm), $\text{SpO}_2 \leq 93\%$ on room air at sea level, ratio of arterial partial pressure of oxygen to fraction of inspired oxygen ($\text{PaO}_2/\text{FiO}_2$) < 300 , or lung infiltrates $> 50\%$ (COVID-19 Treatment Guidelines Panel, 2020).
4. APACHE II score < 20 or establishment of survivability of the patient beyond 48 hours following randomization.
5. Therapies which have been shown to be beneficial and are included in standard COVID-19 treatment guidelines (e.g., those of WHO or NIH, or institutional guidelines) are permitted.
6. Sexually active women of child-bearing potential (WCBP) must be using a medically acceptable method of birth control throughout the study and for at least 1 day following the end of study, and have a negative urine pregnancy test at the Screening visit. A WCBP is defined as a female who is biologically capable of becoming pregnant. A medically acceptable method of birth control includes intrauterine devices in place for at least 3 months, surgical sterilization, or the implant. In patients who are not sexually active, abstinence is an acceptable form of birth control and urine will be tested per protocol. Women who are of nonchild-bearing potential, i.e., post-menopause, must have this condition captured in their medical history. Pregnant women and nursing mothers are excluded from this study.
7. Patient or Legally Authorized Representative (LAR) is available and willing to give written informed consent, after being properly informed of the nature and risks of the study and prior to engaging in any study-related procedures.

Key Exclusion Criteria:

The presence of any of the following excludes a patient from study enrollment:

1. Known sensitivity, allergy, or previous exposure to LSALT peptide.
2. Exposure to any investigational drug or device <90 days prior to entry into study.
3. Treatment with immunomodulators or immunosuppressant drugs, including but not limited to IL-6 inhibitors, TNF inhibitors, anti-IL-1 immunomodulators, and JAK inhibitors within five half-lives or 30 days (whichever is longer) prior to randomization and throughout the study period. However, should any of these treatments become SOC and incorporated into clinical treatment guidelines (*e.g.*, those of WHO or NIH, or institutional guidelines), the treatment is permitted. Further, low-dose oral prednisone (≤ 20 mg/day) and inhaled steroids (*e.g.*, for treatment of asthma) are allowed in the study.
4. Anticipated transfer to another hospital or medical center within 72 hours, which is not a study site.
5. Uncontrolled or poorly-treated active hepatitis B (HBV), hepatitis C (HepC), or HIV infection. Those subjects who are positive for HBV, HepC, or HIV but are well-controlled with low viral loads are allowed to participate in the study:
 - HBV low viral load defined as $<20,000$ IU/mL
 - HepC low viral load defined as $<800,000$ IU/mL
 - HIV low viral load defined as <5000 copies/mL.
6. Participation in another drug or device study at any time during this study, for example:
 - Ulinastatin 200,000 IU or greater
 - High dose intravenous Vitamin C
 - Budesonide and formoterol
 - Bevacizumab to prevent ARDS
 - Dornase alfa to reduce hypoxemia in ventilated trauma patients.
7. As indicated in the inclusion criteria, pregnant female patients are excluded from study. Further, female patients who are nursing are excluded from study.
8. Has any medical condition considered to be clinically significant and could potentially affect patient safety or study outcome, including but not limited to:
 - Acute or chronic kidney disease (stage-4 or -5 renal impairment; eGFR <30 mL/min/1.73 m² or hemodialysis)
 - End-stage malignancy undergoing treatment
 - Immunocompromised patients or those with medical/surgical conditions (*e.g.*, solid organ transplantation) which require chronic immunosuppression

- Chronic hematologic disease which, in the opinion of the PI, prohibits the patient from entering into study
- Acute liver injury with AST and/or ALT levels greater than 3x ULN, unless recent injury (within 2 weeks) likely due to COVID-19 infection
- History of coagulopathy of unknown etiology, as defined by abnormal ACT (only if part of SOC), aPTT, and/or PT/INR values at least 2-fold outside normal limits, and currently present at screening, and/or
- End-stage lung disease, acute lung injury, very severe chronic obstructive pulmonary disease (COPD) as assessed by the GOLD criteria (GOLD Stage IV), or mechanical ventilation.

TEST PRODUCT, DOSE, AND MODE OF ADMINISTRATION:

LSALT peptide or an equivalent volume of commercially-available 0.9% sodium chloride (saline) solution to a volume of 100 mL mini-IV bag by an unblinded Pharmacist or designate. The drug will be infused into the patient through a peripheral 18, 20, or 22 g intravenous catheter over 2 hours and under the supervision of the Principal Investigator. Study drug may also be administered through a central line. Study drug will be administered once daily at a consistent time throughout the study.

DURATION OF TREATMENT: Maximum of 14 days.

DISCONTINUATION FROM TREATMENT:

Reasons for permanent discontinuation of treatment include the following:

- Patient experiences two or more Grade 2 toxicities or one or more Grade 3 or 4 toxicity considered by the PI to be associated with LSALT peptide treatment (CTCAE v5.0, 2017)
- Patient requests to discontinue treatment or patient withdrawal of consent
- PI considers that it is not in the best interest of the patient to continue treatment due to an adverse event.
- Protocol deviation requiring discontinuation of study treatment for safety reasons, and/or
- Pregnancy.

Patients who discontinue treatment for any reason (except withdrawal of consent from study participation) will not be discontinued from the study and will continue to be followed for all assessments until Day 28, or if not possible then for all assessments necessary to determine the value of the primary endpoint at Day 28.

EFFICACY ENDPOINTS:

Primary efficacy endpoint:

- To evaluate the proportion of subjects alive and free of respiratory failure (e.g., need for non-invasive or invasive mechanical ventilation, high flow oxygen [≥ 6 L/minute], or ECMO) and free of the need for continued renal replacement therapy (RRT) on Day 28. The need for continued RRT at Day 28 will be defined as either dialysis in the past 3 days (Day 26, 27, or 28) or an eGFR on Day 28 <10 mL/min/1.73 m².

Secondary efficacy endpoints include:

- All-cause mortality
- The presence and severity of ARDS as an ordinal outcome of the proportion of patients who have none, mild, moderate, or severe ARDS
- Time to each of mild, moderate, and severe ARDS
- The number of ventilation-free days and ECMO-free days
- Time on nasal canula or oxygen mask
- Length of stay in ICU and hospital (admission to discharge)
- Virologic clearance rate
- Worst PaO₂/FiO₂ ratio following enrollment
- Change in PaO₂/FiO₂ ratio
- Vasopressor-free days
- Change from maximal radiographic damage to EOT
- Change in baseline mMRC score
- Change in APACHE II score
- Proportion of patients with extrapulmonary organ dysfunction using the daily SOFA score
- Change in liver function tests (ALT, AST, total bilirubin)
- Change in renal function tests (SCr, eGFR)
- Change in hs-troponin levels
- Change in ACT, aPTT, and/or PT/INR values
- Change in antiviral IgG, IgA, and IgM levels.

Health Outcomes endpoint:

- Total healthcare costs from admission to discharge between treatment groups.

Exploratory Endpoints:

- Change in serum cytokines including IL-1 α , IL-1 β , and ferritin levels, as well as other exploratory biomarkers drawn at the same time as LSALT peptide concentrations.
- Change in baseline antiviral immunoglobulins (IgG, IgM, IgA) at EOS.

SAFETY ENDPOINTS:

- Treatment-emergent adverse events (TEAEs)
- Clinical laboratory tests
- Physical examinations
- Vital signs
- 12-lead electrocardiogram
- Radiologic findings

PHARMACOKINETICS (PK): Blood samples will be obtained at Baseline prior to the start of drug infusion on Day 1, then midpoint (1 hour after start of infusion), and immediately following the daily 2-hour infusions on Days 1, 3, and at EOT regardless of active or placebo therapy. These blood samples will be analyzed for parent LSALT peptide and associated fragments (metabolites). Cytokines will be measured at the same times to assess relationship between drug concentrations and cytokine levels.

STATISTICAL METHODS:

Sample Size: Sixty subjects are planned for enrollment (randomized and treated) in this study.

Efficacy Analyses: Continuous variables will be summarized with descriptive statistics (the number of non-missing values [n], mean, median, standard deviation [SD], minimum, and maximum). All categorical variables will be summarized with frequency counts and percentages, as applicable. Time to event variables will be summarized using Kaplan-Meier survival curves and compared between treatment groups using either Log-rank tests or Cox's Proportional Hazard model adjusting for baseline covariates, as necessary. For continuous variables assessed at multiple time points, a Mixed Model Repeated Measures (MMRM) approach will be used or Analysis of Covariance (ANCOVA) if assessed at a single time point post-baseline. For categorical endpoints Cochran-Mantel-Haenszel (CMH) methods will be used, or a logistic regression approach, in the case of continuous covariates. The primary efficacy analysis population will be the Full Analysis Set (FAS), which will include all subjects randomized who receive any part of at least one infusion of randomized treatment, assigned to treatment group as randomized.

Additional details regarding precise endpoint definitions (including transformations, as applicable), analysis model specifications and α -level control for primary and important secondary endpoints associated with multiplicity will be provided in a separate statistical analysis plan (SAP), to be finalized prior to unblinding the study.

Although significant missing data with respect to the primary endpoint is not anticipated for a study of this duration (due to the nature of the endpoint), methods for handling missing data and intercurrent events, including for secondary endpoints will be specified in the SAP. These methods will be consistent with missing data due to death as having a worst possible outcome.

Safety Analysis:

All patients randomized and who received any part of at least one infusion of randomized treatment will be evaluated for safety according to the treatment actually received. The safety analyses will include evaluation of the incidence of treatment-emergent AEs, SAEs, and AEs leading to discontinuation of study treatment tabulated by Overall, System Organ Class, and Preferred Term using the MedDRA coding system. Additional tables with AEs by severity and relationship to drug as assessed by the PI will be presented. Laboratory data, vital signs, radiologic evidence, drug and cytokine concentrations, and ECGs assessments will be evaluated over time on study using descriptive statistics, including changes from baseline. Shift analyses of relevant clinical laboratory parameters will be produced showing shifts across low, normal, and high categories.

DOCUMENT APPROVAL

This study will be conducted in compliance with the protocol, Good Clinical Practice (GCP) and applicable regulatory requirements.

ARCH BIOPARTNERS REPRESENTATIVE

Signature

[name]

Date 17-March-2021

PRINCIPAL INVESTIGATOR

Signature

Print Name: [name]

18-March-2021

Date

TABLE OF CONTENTS

SYNOPSIS.....	2
1 LIST OF ABBREVIATIONS.....	14
2 ETHICAL CONDUCT OF THE STUDY AND REGULATORY REQUIREMENTS	17
2.1 Institutional Review Board (IRB) or Ethics Committee (EC).....	17
2.2 Ethical Conduct of the Study	17
2.3 Patient Information and Consent	17
3 INTRODUCTION	18
3.1 COVID-19 Background.....	18
3.2 Acute Respiratory Distress Syndrome.....	19
3.2.1 Scoring systems	24
3.3 LSALT peptide	25
3.3.1 Inflammation and Organ Injury	25
3.3.2 Pre-Clinical Data for Dipeptidase-I and LSALT Peptide in AKI	27
3.3.3 Drug Metabolism and Pharmacokinetics.....	29
3.3.4 Toxicology and Safety.....	29
3.3.5 Preliminary Safety in Humans.....	31
3.3.6 Pharmacokinetics	32
3.4 Study Rationale.....	32
3.5 Dose Justification.....	33
4 STUDY OBJECTIVES AND ENDPOINTS.....	34
4.1 Study Objectives.....	34
4.1.1 Primary Objective	34
4.1.2 Secondary Objectives	34
4.1.3 Health Outcomes Objective.....	35
4.1.4 Exploratory Objectives	35
4.2 Study Endpoints.....	35
4.2.1 Primary Efficacy Endpoint	35
4.2.2 Secondary Efficacy Endpoints.....	35
4.2.3 Health Outcomes endpoint:	36
4.2.4 Exploratory Endpoints:.....	36
4.2.5 Safety Endpoints.....	36
5 INVESTIGATIONAL PLAN.....	36
5.1 Overall Study Design and Plan – Description	36
5.2 Number of Patients (Planned).....	37
5.3 Discussion of Study Design.....	38

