Similarly, acute kidney injury (AKI) associated with COVID19 has important clinical implications with more than two thirds of patients experiencing prolonged hospitalization and/or death (Hirsch *et al*, 2020). While the pathophysiology of COVID19-associated AKI is not fully understood, inflammation related to direct viral infection of kidney cells, renal ischemia or systemic illness (sepsis or cytokine storm) are believed to play a role (Battie *et al*, 2020; Diao *et al*, 2020).

Given its favorable toxicology and clinical pharmacology profiles, the administration of LSALT peptide to target lung and kidney inflammation and prevent or minimize ARDS or AKI during a COVID-19 infection has the potential to provide a significant long-term clinical impact. During the course of their disease, approximately 17 – 42% of COVID-19 hospitalized patients develop ARDS within 8 days of admission and almost half of those patients died while hospitalized (Chen *et al*, 2020; Huang *et al*, 2020; Wang *et al*, 2020; Wu *et al*, 2020). 36.6% of patients developed AKI in the series by Hirsch with more than two thirds of patients dying or requiring prolonged hospitalization. Of the patients who were discharged, a large proportion were left with significant kidney dysfunction (Hirsch *et al*, 2020). How many had cleared the virus is unknown from the literature.

Clearly, a therapeutic intervention that prevents life-threatening ARDS is needed. Even a 20 – 30% reduction in ARDS incidence or severity during COVID-19 would have a significant impact on clinical outcomes and health systems, including mortality, critical care, and ventilatory capacity. LSALT peptide has shown activity in animal models of inflammation including lung, kidney, and liver injury in the context of bacterial sepsis and its safety profile has been well-described in healthy adult subjects. Thus, the critical next step is the proof-of-concept Phase 2 study in hospitalized patients with COVID-19. We are attempting to answer the question: “How do we *survive* infections?”

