5.3 Discussion of Study Design

This double-blind, placebo-controlled, proof-of-concept Phase 2 study is designed to evaluate LSALT peptide compared with placebo in a defined number of adult hospitalized patients with the diagnosis of COVID-19. This is a 1:1 randomization comparing 5 mg LSALT peptide daily with matching placebo. LSALT peptide or drug-free saline will begin immediately once the patient meets all inclusion/exclusion criteria at the start of hospitalization and followed with physical and respiratory exams, blood chemistries, coagulation, hematology, ECGs, SARS-CoV-2 tests, CXRs, biomarkers, and PK will be recorded periodically throughout the 28 day study. When clinically indicated, questionnaires (APACHE II, SOFA) will be obtained at Baseline, EOT, and EOS; venous blood gas (VBG) or HCO_3 (bicarbonate) levels may be substituted for arterial blood gas (ABG) if it is SOC or in the patient's best interest, and results in comparable APACHE II and SOFA scores (Brown *et al*, 2016). Other questionnaires (Berlin Definition and modified Medical Research Council Dyspnea Scale) will be assessed at Baseline, Day 3, EOT, and EOS. Patients will be maintained on SOC, including prophylaxis or treatment for VTE, per institutional guidelines throughout the study. Dosing will end on Day 14, or at cure or increasing severity of ARDS, or at death. Patients will be followed clinically, and safety and efficacy measures will be recorded at end of study (EOS; Day 28) or death, whichever occurs first.

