8 STUDY PROCEDURES AND FLOW CHART

8.1 Study Flow Chart

Calendar	Admission ^a	Admission ^b	Treatment Period	Treatment Period	EOT	EOS
Day	1	1	1 – 14 (max)	3	Variable	28±3
Sign informed consent	X					
Assign screening number	X					
Inclusion/exclusion criteria	X					
Review demographics	X					
Review medical history	X					
Concomitant meds ^c	X		X	X	X	X
Physical exam ^c	X		X	X	X	X
Respiratory exam ^c	X		X	X	X	X
Urine pregnancy in WCBP	X					
Clinical labs/Urine tests ^{c,d}	X			X	X	X
12-lead ECG ^e	X			X	X	X
Vital signs ^{c,f}	X		X	X	X	X
eGFR ^{b,d}	X			X	X	X
SARS-CoV-2 testing swabs ^{c,g}	X			X	X	X
Chest x-ray ^h		X		X	X	X
PK and biomarker samples ⁱ		X		X	X	X
Randomization		X				
Study drug administration		X	X	X	X	X
AE assessments		X	X	X	X	X
SARS-CoV-2 IgG, IgA, IgM levels		X				X
Berlin Definition ^{j,k}		X		X	X	X
SOFA score ^{j,l}		X		X	X	X
mMRC score ^{j,m}		X		X	X	X
APACHE II score ^{j,n}		X		X	X	X
Health Outcomes						X

^a Screening to determine eligibility (prior to randomization)

^b Baseline after Screening and prior to the start of study drug unless otherwise indicated.

^c Performed at Screening, Day 3, and EOT prior to drug administration, and at EOS.

^d Hematology, biochemistry, coagulation, and urinalysis will be obtained and eGFR will be calculated (Appendix 2), and when clinically indicated.

^e 12-Lead ECG (supine) will be recorded at time 0 (pre-dose) at Screening, Day 3, EOT, and at EOS (only if clinically indicated). Also, an ECG will be obtained during the study when clinically indicated.

^f Blood pressure (supine), pulse rate (supine), body temperature, respiration rate (supine), actual body weight (kg), and height (cm). Note: Height will only be measured at Screening.

^g Swabs (nasal, throat, sputum, or lower respiratory tract) at Screening, Day 3, EOT, and EOS.

^h Chest x-rays at Baseline (Day 1), Day 3, at time of clinical improvement, at EOT, and EOS. A chest x-ray will also be obtained if clinically warranted and recorded in the eCRF.

ⁱ Blood draws at Baseline pre-dose, at the mid-point (1 hr) and at the end of 2-hr infusion of study drug on Days 1, 3, and EOT, and a single blood draw at EOS.

^j Obtained at Baseline, Day 3, when clinically indicated, at EOT, and at EOS.

^k Appendix 3

^l Appendix 4

^m Appendix 5

ⁿ Appendix 6

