8.2.4 During Treatment Period (Day 3 and EOT, and when clinically indicated)

- Document concomitant drugs, including drug name, dose, and frequency
- Perform physical examination including respiratory exam
- Obtain chest x-ray on Day 3, in the event of clinical improvement, and at EOT, and when clinically indicated
- 12-lead ECG
- Laboratory tests including hematology, biochemistry, coagulation, and urinalysis on Day 3, EOT, and if clinically indicated
- Measure vital signs, including blood pressure (sitting), pulse rate, body temperature, respiration rate, and actual body weight (kg) daily or as clinically indicated – note: no need to document height.
- Calculate eGFR
- Administer IV drug over 2 hours
- Collect blood samples (5 mL each) at mid-point and end of the 2-hour drug infusion for PK and biomarker analysis. Prepare the samples per Section 7.3.2.2.
- Review and record any TEAEs
- Swab nasal, throat, sputum, or lower respiratory tract source for SARS-CoV-2 on Days 4, 7, 10, and 14 (if necessary).
- Complete the (1) Berlin Definition (Appendix 3), (2) SOFA score (Appendix 4), and (3) modified Medical Research Council Dyspnea Scale (Appendix 5), and (4) APACHE II score (Appendix 6; only if clinically indicated).

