8.2.5 End of Treatment (EOT)

The EOT visit refers to the completion of the last dose of study drug. All study assessments outlined during the Treatment Period are to be performed. For a complete list of assessments, refer to the Study Flow Chart.

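### Time to each ARDS grade goes to Kaplan-Meier and log-rank or Cox, but Berlin grading has three fixed post-baseline time points, an undefined unscheduled trigger and no grade-specific onset date

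*Combined protocol and SAP*

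**What the plan says.** **Endpoint and analysis.** The secondary endpoints (synopsis, 4.2.2, 7.1.2) include "Time to each of mild, moderate, and severe ARDS", and the secondary objectives (synopsis, 4.1.2) add incidence by grade. The synopsis and Section 9.3.2 state: "Time to event variables will be summarized using Kaplan-Meier survival curves and compared between treatment groups using either Log-rank tests", or a Cox model. Precise endpoint definitions are deferred to a separate SAP, which is not in the text supplied.

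**Schedule.** The synopsis and Sections 5.1 and 5.3 give the Berlin form four time points: "Other questionnaires (Berlin Definition and modified Medical Research Council Dyspnea Scale) will be assessed at Baseline, Day 3, EOT, and EOS". Footnote j of the flow chart (8.1) is wider: "Obtained at Baseline, Day 3, when clinically indicated, at EOT, and at EOS". The heading of Section 8.2.4, whose list contains the Berlin item, agrees with the footnote: "During Treatment Period (Day 3 and EOT, and when clinically indicated". No section says what makes an assessment clinically indicated. The list for the other treatment days (8.2.3) has a respiratory examination but no Berlin item.

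**When EOT falls.** Section 8.2.5: "The EOT visit refers to the completion of the last dose of study drug". Section 5.3: "Dosing will end on Day 14, or at cure or increasing severity of ARDS, or at death". The discontinuation list in Section 5.4.3, repeated in the synopsis, names neither cure nor increasing ARDS severity. EOS is Day 28 ± 3.

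**Expected timing.** Section 3.4 expects about 17-42% of hospitalised patients to "develop ARDS within 8 days of admission and almost half of those patients died while hospitalized".

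**The concern.** Kaplan-Meier, log-rank and Cox analyses of time to a grade need the date on which that grade was first met. The protocol assures a grade only at Day 3, at EOT and at EOS. An episode that begins and resolves between two of these, with no unscheduled assessment, is never graded. One that persists is dated to the next assessment.

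The period in which Section 3.4 expects onset lies largely between Day 3 and a Day 14 EOT. EOT also varies by patient and, under Section 5.3, can follow from the course of the disease, so the chance of detecting ARDS can depend on when dosing ended.

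ARDS is the condition named first in the trial's title. Lost or late-dated events would weaken the endpoints closest to its purpose. A SAP written later can choose a test, but it cannot supply dates that were never collected.

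**Working it through.** The documents give no figure for ARDS detection or dating, so there is none to reproduce.

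**1. Gaps between fixed assessments** (8.1, 8.2.5, 8.2.6)
- EOT on Day 14: 3 − 1 = 2 days, 14 − 3 = 11 days, then 28 − 14 = 14 days (11 to 17 with the ± 3 window).
- EOT on Day 7: 2 days, 4 days, then 21 days (18 to 24 with the window).

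**2. One gap, fixed assessments only.** For onset uniform in a gap of length L and fixed duration D, the missed share is max(0, (L − D)/L). If the episode persists, the mean dating delay is L/2. In the 11-day gap:
- D = 5: 6/11 = 55% missed
- D = 7: 4/11 = 36%
- D = 10: 1/11 = 9%
- Persistent: none missed, mean delay 11/2 = 5.5 days.

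**3. Whole course, with unscheduled capture.** All inputs here are assumptions: onset uniform on Days 2-12; lognormal duration with median 4, 7 or 10 days (sigma 0.6); assessments on Days 3, 14 and 28; deaths ignored. Simulation with no unscheduled capture gives a missed share m and a mean delay d among detected episodes. If a share c of episodes is instead caught at onset, the missed share is (1 − c)m and the mean delay is (1 − c)(1 − m)d / [1 − (1 − c)m].

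| Capture c | Missed, median 4 / 7 / 10 days | Mean delay when detected (days) |
|---|---|---|
| 0% | 63% / 38% / 22% | 3.4 / 4.6 / 5.2 |
| 50% | 32% / 19% / 11% | 0.9 / 1.8 / 2.3 |
| 80% | 13% / 8% / 4% | 0.3 / 0.6 / 0.9 |
| 90% | 6% / 4% / 2% | 0.1 / 0.3 / 0.4 |

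**4. Number of cases.** At the rates in Section 3.4, 60 patients yield 0.17 × 60 ≈ 10 to 0.42 × 60 ≈ 25 ARDS cases over all grades. The time-to-grade analyses divide these further, so a few lost events matter.

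**5. Dependence on EOT** (median duration 7 days, same ARDS course in both arms)
- Onset Days 2-12, c = 0: EOT on Day 7 detects 51% and EOT on Day 14 detects 62%; ratio 0.51/0.62 = 0.82.
- Onset Days 1-9, c = 0: 74% and 57%; ratio 0.74/0.57 = 1.30.
- Onset Days 2-12, c = 80%: 1 − 0.2 × 0.49 = 90% and 1 − 0.2 × 0.38 = 92%; ratio 0.98.

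Detection can depend on EOT, but the direction turns on the assumed onset window, and the effect nearly vanishes when unscheduled capture is high.

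**The case against.** **Unscheduled assessments may catch most onsets.** Berlin ARDS requires PEEP or CPAP of at least 5 cm H₂O (Appendix 3), and mechanically ventilated patients are excluded at entry. Onset is therefore a visible escalation of support in a hospitalised patient, and zero capture is the least plausible row of the table. This stands. It limits the size of the problem but does not remove it: the provision has no trigger and is absent from the synopsis, 5.1 and 5.3.

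**Worsening can itself bring an EOT assessment** (5.3 with 8.2.5). This stands in part. Worsening is not first onset, the provision works only during dosing, and Section 5.4.3 does not list it. It also ties the timing of an assessment to the outcome.

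**Adverse events are recorded with start dates** (7.3.1.2). True, so onset dates are not wholly absent. Those records carry a CTCAE severity and not a Berlin grade, and nothing links them to this endpoint.

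**The SAP may define onset.** It may, so the lack of an interval-censored method in the text supplied is not proof that none was planned. The gap that remains is in data collection.

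**The power at stake is small in any case.** If ARDS fell from 42% to 21%, log-rank power with 30 per arm would be about 41% with true dates, against 15-30% with visit dates and no unscheduled capture. For the 20-30% reduction that Section 3.4 discusses, power is only about 10-17% even with perfect dates and 8-11% with visit dates. The sample size was not based on power (9.1). This stands, and it argues for a proportionate remedy.

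**Conclusion.** The gap is real and worth closing, but its size is unknown. The documents assure Berlin grading at three post-baseline points only, add unscheduled assessments in some sections and not in others, and provide no grade-specific onset date for a time-to-event analysis. Under the assumptions in the working, the missed share runs from 22-63% with no unscheduled capture to 2-6% at 90% capture. Persistent episodes would be dated late, not missed.

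Two stronger readings are tempting and are not supported:
- A reader might infer that many episodes must be missed and the rest dated days late. That follows only if unscheduled and EOT assessments catch few onsets, which the documents do not say.
- A reader might infer a false treatment benefit of about 18% (1 − 0.82) if EOT falls earlier on active drug, and set it beside the 20% reduction in Section 9.3.6.1. The sign reverses when onset is placed on Days 1-9, and that 20% concerns the primary endpoint, not ARDS.

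The affected endpoints are secondary. The Day 28 primary endpoint does not use the Berlin form.

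**What to change.** - **Data.** Add one eCRF item, completed at EOS or death from existing hospital records (blood gases, PEEP or CPAP settings, imaging): the first calendar date on which each Berlin grade was met between randomisation and Day 28. Use it for ARDS incidence and for time to each grade. Detection then depends far less on when dosing stopped or on what a site regards as clinically indicated.
- **Analysis.** State in the SAP that these dates define onset, and name an interval-censored test for cases where onset is known only to lie between two assessments. That test alone is not enough, because standard versions assume that assessment times do not depend on the outcome, and under Section 5.3 EOT may.
- **Wording.** Align the Berlin schedule in the synopsis, 5.1 and 5.3 with footnote j of the flow chart. Reconcile Section 5.3 with the discontinuation list in 5.4.3 on when dosing ends.

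The cost is one eCRF page, chart abstraction for 60 patients and some SAP text, with no new test or visit. The limitation is that the dates will be only as fine as the frequency of blood gases in routine care.
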